## **6. Co-enrolment**

Co-enrolment in other studies, either observational or experimental, will only be permitted following approval by the Principal Investigator.

## **7. Study Intervention:**

Antiretroviral therapy will be initiated when any one of the following criteria are met:

- reach a CD4+ count of less than 350 cell/mm^3
- acquire an AIDS defining illness
- become pregnant

At enrolment women in each of the three study populations will be assigned randomly to one of the two following antiretroviral regimens

Intervention Arm:	Tenofovir, Lamivudine and Efavirenz (TDF/3TC/EFV)
Control arm:	Zidovudine, Lamivudine and Efavirenz (ZDV/3TC/EFV)

### **7.1 Treatment considerations:**

- The current South African antiretroviral treatment guidelines, 2010, prescribe as first line regimen for all new patients needing treatment, including pregnant women, initiation on Tenofovir,

Lamivudine or Emtricitabine, and Efavirenz or Nevirapine. Patients with a contraindication to tenofovir should be initiated on zidovudine [25].

- In this study abacavir will be reserved as an alternative nucleotide reverse transcriptase inhibitor (NRTI) for drug switches if required or if there are contra-indications to using Zidovudine.
- If a participant becomes pregnant during the study follow up she will be switched from efavirenz to nevirapine if still in the first trimester.
- For patients with TB co-infection a regimen containing efavirenz is the preferred choice [25].
- Participants who are found to be anaemic at screening will be commenced on haematinics and haemoglobin will be re-evaluated prior to enrolment
- Participants found to have a creatinine clearance of <60ml/min at screening will be investigated and re-assessed over three months. If the creatinine clearance remains <60ml/min, then the potential participant will not be eligible for this study
- Participants failing first line regimen because of virological failure or virological together with immunological or clinical failure will be commenced on an appropriate second line regimen. Participants will be commenced on a NRTI not used in the first line regimen together with lamivudine or emtricitabine and lopinavir/ritonavir [25].

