## Open Label Randomized Controlled Trial to Assess the Impact of prophylactic exposure to tenofovir gel on the efficacy of subsequent tenofovir-containing antiretroviral therapy on viral suppression

### STUDY SCHEMA

Purpose:	To determine whether prophylactic exposure to tenofovir gel alters the therapeutic response to a tenofovir containing antiretroviral regimen				
Study design:	Open label, two-arm, randomised controlled trial				
Study population:	Women who become infected with HIV while participating in the CAPRISA 004 and CAPRISA 008 trials. There are 3 study populations: Study population 1: HIV positive women from the CAPRISA 004 tenofovir gel arm and HIV positive women from the clinical trial tenofovir gel provision arm of CAPRISA 008 Study population 2: HIV positive women in the placebo arm of CAPRISA 004 Study population 3: HIV positive women from the family planning service arm of CAPRISA 008				
Study sites:	CAPRISA eThekweni and CAPRISA Vulindlela clinics.				
Study duration:	3 years				
Study intervention:	Enrolled women will be initiated on their assigned antiretroviral therapy regimen when they reach any of the following criteria: 

• reach a CD4+ count of less than 350 cell/mm^3

• acquire an AIDS defining illness

• become pregnant - women in any of the three study populations who become pregnant during follow-up will be initiated on their assigned treatment regimen, as appropriate, for prevention of mother-to-child transmission of HIV.

 
At enrolment women in each of the three study populations will be assigned randomly to one of the two following antiretroviral regimens
 

Intervention Arm:	Tenofovir, lamivudine and efavirenz	

Control arm:	Zidovudine, lamivudine and efavirenz	

	Intervention Arm:	Tenofovir, lamivudine and efavirenz	Control arm:	Zidovudine, lamivudine and efavirenz
Intervention Arm:	Tenofovir, lamivudine and efavirenz				
Control arm:	Zidovudine, lamivudine and efavirenz				
Sample size:	The projected sample size is 90 women. The number of women in each stratum is as follows: Study population 1: n = 40 Study population 2: n = 30 Study population 3: n = 20				

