### 5. Study Population:

Women who become infected with HIV while participating in the CAPRISA 004 and CAPRISA 008 trials.

There are 3 study populations:

- Study population 1:* HIV positive women from the CAPRISA 004 tenofovir gel arm and HIV positive women from the clinical trial tenofovir gel provision arm of CAPRISA 008
- Study population 2:* HIV positive women in the placebo arm of CAPRISA 004
- Study population 3:* HIV positive women from the family planning service arm of CAPRISA 008

Women in any of the three study populations who become pregnant during follow-up will be initiated on their assigned treatment regimen, as appropriate, for prevention of mother-to-child transmission of HIV.

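### First-trimester pregnancy starts an efavirenz regimen under Sections 5 and 7 but requires a switch off efavirenz under Section 7.1, depending only on whether study treatment has begun

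*Protocol*

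**What the plan says.** Four places in the protocol deal with ART in pregnancy.

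- **Section 7 (Study Intervention).** "Antiretroviral therapy will be initiated when any one of the following criteria are met", and the third criterion is simply "become pregnant". The two randomised regimens follow. One combines tenofovir and the other zidovudine with the same two drugs, lamivudine and efavirenz. No gestation is mentioned.
- **Study Schema.** The same trigger, with the addition that "women in any of the three study populations who become pregnant during follow-up will be initiated on their assigned treatment regimen, as appropriate".
- **Section 5 (Study Population).** The rule is repeated for women "who become pregnant during follow-up will be initiated on their assigned treatment regimen, as appropriate, for prevention of mother-to-child transmission of HIV".
- **Section 7.1 (Treatment considerations).** "If a participant becomes pregnant during the study follow up she will be switched from efavirenz to nevirapine if still in the first trimester". A neighbouring bullet says: "For patients with TB co-infection a regimen containing efavirenz is the preferred choice". The first bullet of the section summarises national guidance, under which first-line treatment, including in pregnancy, may contain either efavirenz or nevirapine.

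Three other places fix the context. Section 5.4 and note 1 to Appendix 1 make enrolment and ART start coincide. Section 5.2 does not list pregnancy as an exclusion. Appendix 1 schedules a pregnancy test at every visit.

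**The concern.** The protocol expects to enrol women because they are pregnant, and it tests for pregnancy throughout, so first-trimester cases will arise both at ART start and on treatment. For those already on treatment it gives a firm instruction about efavirenz that depends on gestation. For those starting treatment it gives a regimen containing efavirenz and no word on gestation. Nothing explains why the two situations should differ, or says that the difference is intended.

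Two sites could therefore treat similar women differently, each believing that it follows the protocol, in a matter that concerns mother and fetus.

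**Working it through.** The check is a comparison of text. It involves no power, rate or sample size, so no arithmetic applies.

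**Step 1: a woman who starts ART because she is pregnant.** Women are followed in CAPRISA 002 until they are eligible for ART and are then referred to this trial (Section 5.3). Pregnancy alone meets the criterion (Section 7), and it does not exclude her (Section 5.2). Enrolment, randomisation and ART start fall together (Section 5.4; Appendix 1, note 1). If she is in the first trimester, Section 7 gives her the regimen of her arm, which contains efavirenz in either case. The Section 7.1 bullet does not literally reach her: she did not become pregnant during study follow-up, and before ART starts she has no efavirenz to be switched from.

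**Step 2: a woman already on study treatment who is found to be in the first trimester.** Section 7.1 applies directly, and efavirenz is replaced by nevirapine.

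**Step 3: the two side by side.**

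| | Pregnant at ART start, first trimester | Becomes pregnant on study treatment, first trimester |
|---|---|---|
| Governing text | Schema, Sections 5 and 7 | Section 7.1 |
| Limit by gestation | None stated | First trimester |
| Efavirenz, as written | Started | Replaced by nevirapine |

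**Step 4: does the qualifier settle it?** *As appropriate* stands in the Schema and Section 5 but not in Section 7. It is nowhere defined and nowhere tied to trimester. It leaves room for judgement without saying how that judgement should be used.

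**Step 5: what does follow-up mean?** The Schema and Section 5 use the term for women who are about to start ART.
- If it means follow-up in this trial, those women are already on ART and there is nothing to initiate. The same trigger then leads to starting the efavirenz regimen in Section 5 and to leaving efavirenz in Section 7.1.
- If it means follow-up in CAPRISA 002 before enrolment, Sections 5 and 7.1 address different women. The wording no longer collides, but the difference in Step 3 remains.

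The inconsistency survives either reading.

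**Step 6: does it reach the primary endpoint?** Sections 2.4 and 9.1 count only regimen changes made for treatment failure, so a pregnancy switch is not an event. Section 9.3 makes the primary analysis intention-to-treat. The arms differ only in tenofovir versus zidovudine, and the switch rule makes no distinction between them.

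**The case against.** The strongest defence is that the sections can be read together without breaking either. Starting a regimen can apply only to a woman not yet on ART, and switching from efavirenz only to a woman taking it. On that reading no single patient receives two opposing orders. Section 7.1 itself supplies a nevirapine option, and its guideline bullet mentions one, so *as appropriate* has something to refer to. Section 5.2 also lets the investigator exclude a woman for whom participation would be unsafe.

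Much of this stands, and it rules out several stronger readings that a reader might infer:

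- **That sites must break one instruction to follow another.** This is not supported. The sections can be assigned to different women.
- **That opposite treatment is certain in practice.** This is not supported. It is what the literal text produces, but the qualifier leaves clinicians room.
- **That the TB and pregnancy bullets contradict each other outright.** One is a rule and the other a preference, and a preference can yield. What is missing is a statement of which ranks first.
- **That the ancillary objective is undermined.** Section 2.3 concerns a regimen containing tenofovir. Replacing efavirenz with nevirapine does not change that.
- **That per-protocol and as-treated status is left undefined.** Those definitions properly belong in the statistical analysis plan.
- **That a count of affected women can be given.** Assuming 10 to 20% of the 90 planned women gives 9 to 18, but the protocol states no pregnancy rate. Such a figure would also pool women pregnant at ART start with women who conceive on treatment, whom Section 7.1 already covers. Nor would every such pregnancy yield the 6-week infant PCR that the ancillary endpoint needs.

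The defence does not supply an instruction for a woman who starts ART in the first trimester, or a reason for treating her differently from one already on treatment. Using the discretionary exclusion for such women would undercut a stated criterion for starting ART.

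**Conclusion.** The point holds as an inconsistency in the treatment rules. As written, women at the same gestation receive opposite instructions on efavirenz according to whether study treatment has begun, and no text explains the difference or defines the qualifier that might soften it. The loose use of follow-up in the Schema and Section 5 makes the intended scope harder to recover.

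Its weight lies in patient safety and in consistency between sites. The expected effect on the primary intention-to-treat comparison is small, for the reasons in Step 6. How many women are affected cannot be derived from the protocol. The conclusion rests on a literal reading. It takes no position on which instruction is clinically right, or on whether the two situations ought to be treated alike.

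**What to change.** Reconcile the Study Schema and Sections 5, 7 and 7.1 so that the instruction for first-trimester pregnancy is explicit and consistent, both at ART initiation and during follow-up. The revised text should:

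1. state what applies to a woman in the first trimester when ART is started, and either define *as appropriate* or remove it;
2. say which follow-up is meant in the Schema and Section 5 (CAPRISA 002 before enrolment, or this trial);
3. state how the pregnancy and TB bullets in Section 7.1 rank when both apply.

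The investigators decide the clinical content. The cost is a wording amendment through the approval route in Section 13.1. It needs no extra participants, visits or tests, and no change to the primary endpoint.

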## **8. Summary of Assessments:**

### **8.1 Counselling**

Participants will receive risk reduction counselling at enrolment and all scheduled follow up visits. Adherence support counselling (ASP) will be provided at screening and at ART initiation. ASP will be provided during follow up if there is any indication that a participant may have low compliance to ART.

### **8.2 Behavioural Assessment**

Questionnaires on HIV risk and quality of life will be administered at specified visits according to the schedule of evaluations.

### **8.3 Clinical assessment**

Participants will have a medical history taken at every scheduled visit. A physical examination, including vital signs will also be done at every scheduled visit. A morphological examination will be done at enrolment and 6 monthly thereafter, Pelvic examinations will be done on visits requiring genital specimen collection or if clinically indicated. Participants will be monitored for side effects experienced following ART initiation, compliance on ART and the development of new opportunistic conditions. All grade 3 and 4 adverse clinical events will be documented and graded according to the DAIDS toxicity grading system. Serious adverse events including deaths will be reported to the BREC in writing. Pregnancies will be documented and outcomes including HIV status of the infant will be followed up. All clinical events will be managed by the study clinician. Participants will be referred to their a local hospital for any problem that cannot be managed at the clinical research site. Clinical data will be captured on CRFs.

### **8.4 Laboratory Assessment**

Laboratory assessments will follow the schedule of evaluations:

- Urine pregnancy test at every visit
- FBC (full blood count), U+E(urea and electrolytes) and Creatinine at baseline and 6monthly intervals
- Cholesterol, LFT (liver function tests) iron studies, Vitamin B12 and folate and calcium, magnesium phosphate at baseline and yearly intervals
- Blood specimens for STI screen at baseline and yearly intervals.
- Genital specimens for STI screen at baseline and yearly intervals
- Genital specimens for mucosal immunology at every visit
- Blood for virology , immunity assays, storage, resistance testing and storage to be collected at every visit

## 9. Statistical Considerations

### 9.1 Sample Size:

The total number of women with HIV infection in the CAPRISA 004 and CAPRISA 008 studies is anticipated to be approximately 120 in the tenofovir gel exposed group. In addition 60 participants seroconverted in the 004 study on the placebo treatment arm.

If 50% of these participants need to be initiated on ART within the next 3 years, we would be able to randomise approximately 60 participants who were exposed to tenofovir gel to ART assignment. We also anticipate that 30 participants who seroconverted on the placebo arm will be eligible for randomisation to treatment assignment in the next 3 years (Table 1).

There are 3 study populations:

*Study population 1:* HIV positive women from the CAPRISA 004 tenofovir gel arm and HIV positive women from the clinical trial tenofovir gel provision arm of CAPRISA 008

*Study population 2:* HIV positive women in the placebo arm of CAPRISA 004

*Study population 3:* HIV positive women from the family planning service arm of CAPRISA 008

Participants will be randomised in each of the tenofovir gel exposed groups and the placebo gel exposed groups to either a tenofovir containing antiretroviral regimen or a tenofovir-sparing antiretroviral regimen.

The primary treatment outcome, treatment failure (treatment failure includes viral load > 50 copies/mL at 12 months, regimen changes for treatment failure within the first 12 months or death within the first 12 months), will be analysed in four different comparisons.

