## 3. Methods

### 3.1 Study Overview

This study is an open label, two-arm, randomised control trial comparing treatment outcomes in women previously exposed to tenofovir gel at the time of HIV acquisition, who are randomised to either a tenofovir containing or a tenofovir-sparing antiretroviral treatment regimen. Comparisons in treatment outcomes will also be made between tenofovir gel exposed and tenofovir gel unexposed women following tenofovir containing antiretroviral treatment initiation. Approximately 90 women who have seroconverted while in the active or placebo arms of the CAPRISA 004 (Phase IIb Trial to Assess the Safety and Effectiveness of the Vaginal Microbicide 1% tenofovir Gel for the Prevention of HIV Infection in Women in South Africa) study and the CAPRISA 008 (Phase IIIb Open-Label Randomized Controlled Trial to Assess the Effectiveness and Safety of Tenofovir Gel Provision through Family Planning Services in KwaZulu-Natal, South Africa) study will be enrolled. Enrolment into the study will coincide with eligibility for ART initiation. Following enrolment, at which the assigned ART regimen is initiated, women will be followed up at week 1, month 1, 3, 6, 12, 18, 24, 30 and 36. The primary endpoint is the antiretroviral treatment failure rate at 12 months. Treatment failure is defined as viral load > 50 copies/ml, antiretroviral regimen changes for treatment failure or death. In addition CD4+ monitoring, viral resistance testing, adverse event reporting and blood and mucosal immunology assays will be conducted to fulfil the secondary objectives of the study. The anticipated total study duration is approximately 36 months of follow-up after ART initiation.

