#### Power

Comparison A: We anticipate that there will be 30 and 30 participants in the two arms.

Comparison B: We anticipate that there will be 20 and 10 participants in the two arms.

Comparison C: We anticipate that there will be 30 and 15 participants in the two arms.

Comparison D: We anticipate that there will be 30 and 15 participants in the two arms.

Power for Comparison A:

A Fisher's exact test with a 0.05 two-sided significance level will have 70% power to detect the difference between a Group 1 proportion, of 0.9 and a Group 2 proportion, of 0.6 when the sample size in the two groups is 30.

Power for Comparison B:

A Fisher's exact test with a 0.05 two-sided significance level will have 25% power to detect the difference between a Group 1 proportion, of 0.9 and a Group 2 proportion, of 0.6 when the sample sizes are 10 and 20, respectively.

Power for Comparison C and D:

A Fisher's exact test with a 0.05 two-sided significance level will have 43% power to detect the difference between a Group 1 proportion, of 0.9 and a Group 2 proportion, of 0.6 when the sample sizes in the two groups are 15 and 30 respectively.

**Table 1:** Statistical power estimates for comparison A based on a range of sample sizes and potential treatment failure rates

Sample size	Proportion with treatment failure			
	0.10 vs 0.30	0.10 vs 0.40	0.05 vs 0.40	0.10 vs 0.50
40/30	44	77	93	94
30/30	37	70	89	91
30/25	34	64	86	86
30/20	28	57	79	82
40/15	28	55	77	79
30/15	22	47	68	72
30/10	15	34	53	56
20/15	18	41	59	67

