**9.3 Data analysis plan**

A Statistical Analysis Plan (SAP) will outline the statistical analyses. The following is a summary of the planned analyses. Any deviations to be made from this summary plan will be documented in the detailed SAP.

A Fisher's exact test will be used to compare the proportion of participants with treatment failure in each of the two arms. We will also do a stratified Mantel Haenszel test where the stratum is the study arm a participant who seroconverted while randomised to tenofovir was in (004, 008 CAPRISA arm or 008 family planning arm). Placebo arm patients will not be stratified.

In addition, treatment failure at 24 and 36 months will be compared between the treatment arms using the same statistical methods as for the primary comparison at 12 months.

All primary analyses will be performed on an intention-to-treat (ITT) basis with additional analyses performed on the per protocol and as treated populations. For the ITT analysis, participants will be analysed according to the study arm, even if the participant did not follow the assigned procedures. The only participants excluded from this primary analysis population will be women with no post-randomisation visit and no data collected. All primary and secondary analyses will be two-sided and will be performed at the 0.05 level of significance.

The analyses of secondary objectives will be described in detail in the SAP.

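### The protocol tests the primary outcome in four comparisons at 0.05 each and refers to a single primary comparison without naming it; the overview implies A, the primary objective reads as C

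*Protocol*

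**What the plan says.** Protocol section 9.1 states that the primary treatment outcome, failure by 12 months, "will be analysed in four different comparisons". Each has its own hypothesis and none is ranked:

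- **A:** tenofovir-containing against tenofovir-sparing regimen, in gel-exposed women (populations 1 and 3).
- **B:** population 1 against population 3, among women on the tenofovir regimen. The question is the HIV-testing interval while on gel.
- **C:** gel-exposed against unexposed women on the tenofovir regimen.
- **D:** gel-exposed against unexposed women on the sparing regimen, with a hypothesis of no influence.

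The Power subsection gives each comparison its own figure at two-sided 0.05: 70% for A, 25% for B, and 43% for C and D. Table 1 covers A only.

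Section 9.3 adds: "All primary and secondary analyses will be two-sided and will be performed at the 0.05 level of significance". It also says that the 24- and 36-month analyses will follow the methods of the primary comparison at 12 months. That is in the singular, and the comparison is not identified.

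The Study Overview (3.1) describes the trial first as the regimen comparison in gel-exposed women, then says: "Comparisons in treatment outcomes will also be made between tenofovir gel exposed and tenofovir gel unexposed women". Primary objective 2.1 asks whether gel exposure at infection changes the later response to a tenofovir regimen.

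**The concern.** A and C answer different questions. A asks whether the tenofovir regimen does worse or better than the sparing regimen in women who had used the gel. C asks whether gel users on tenofovir fare differently from non-users on tenofovir. They can disagree, for example through an ordinary difference between regimens that has nothing to do with gel exposure. The protocol assumes one primary comparison and gives conflicting signals about which it is, so the choice could be made after the data are seen in an open-label trial.

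Four unranked tests at 0.05 can also take the overall false-positive rate above 5%. How far depends on the conservatism of Fisher's test in these small groups, so it has to be computed for this design.

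**Working it through.** **1. Which comparison is primary?**

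| Place in protocol | Points to |
|---|---|
| 2.1 Primary Objective | C |
| 3.1 Study Overview | A as the design; C (exposed against unexposed, on tenofovir) as an addition |
| 9.1 Comparisons A to D | none ranked |
| 9.1 Power | each powered at 0.05; Table 1 for A only |
| 9.3 Data analysis plan | one primary comparison, unnamed; wording about treatment arms suits A |

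Randomisation (9.2) assigns the regimen within study population. Only A contrasts randomised regimens. B, C and D contrast groups defined by the earlier trial and arm in which the woman became infected.

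**2. Reproducing the stated powers.** Group sizes come from the Power subsection of 9.1: 30 against 30 for A, 20 against 10 for B, and 30 against 15 for both C and D. Proportions are 0.9 against 0.6, that is, failure of 0.10 against 0.40. Power is the sum of the two binomial probabilities over all tables that Fisher's test rejects.

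| Rejection rule | A | B | C, D |
|---|---|---|---|
| Stated | 70% | 25% | 43% |
| Smaller one-sided p ≤ 0.025 | 70.5% | 25.4% | 43.5% |
| Usual two-sided p ≤ 0.05 | 70.5% | 30.0% | 52.3% |

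The first rule reproduces all the stated figures, so each comparison was powered at the full 0.05 with nothing set aside for the others.

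**3. Nominal overall error.** If the four tests were independent and of exact size, it would be 1 − 0.95⁴ = 18.5%; the upper bound is 4 × 0.05 = 20%. The comparisons share arms. For A and C, which share the 30 exposed women on tenofovir, the correlation is (1/30) / √[(1/30 + 1/30)(1/30 + 1/15)] = 0.41. For A and D it is −0.41. With this overlap the nominal figure is 17.8%. None of these allows for the conservatism of Fisher's test.

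**4. Realised overall error.** There were 1,000,000 simulated trials per failure rate, with 20/20, 15/15 and 10/10 women in populations 1, 2 and 3 and one common failure rate throughout. Results vary by about 0.1 point between runs.

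| Common failure rate | Any of A-D, rule matching stated powers | Any of A-D, usual Fisher | A or C, matching rule | A or C, usual Fisher |
|---|---|---|---|---|
| 5% | 0.5% | 2.6% | 0.3% | 1.1% |
| 10% | 2.1% | 6.1% | 1.4% | 2.9% |
| 20% | 5.7% | 9.6% | 3.5% | 4.9% |
| 30% | 7.9% | 11.4% | 4.5% | 5.5% |
| 40% | 8.7% | 11.0% | 4.6% | 5.4% |
| 50% | 9.2% | 10.0% | 5.1% | 5.3% |

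Without D, the maximum is about 7% (matching rule) or 8.5% (usual Fisher). The additional Mantel-Haenszel test in 9.3 is not counted.

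**5. Price of adjusting instead.** With Bonferroni, 0.05/4 = 0.0125 per test, power falls to 49% (A), 9% (B) and 22% (C, D) under the matching rule.

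**The case against.** The strongest reply is that A is already primary in substance. The design has two arms, the regimens. The sentence in 9.3 on the primary comparison concerns treatment arms, the overview introduces exposed against unexposed as an addition, and Table 1 is for A. This stands as far as it goes: A is implied. It is not labelled, however, and the one statement that should settle the matter, objective 2.1, reads as C.

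A second reply is that multiplicity detail belongs in the SAP, which is not at hand. The absence of an adjustment is indeed no finding by itself. But the protocol fixes four unranked comparisons and 0.05 for each, and its own sections conflict on which one leads.

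A third reply concerns size. A reader might infer a false-positive rate near 18.5-20%, or that a positive claim could be built on any of the four. The documents support neither. The specified test is Fisher's, whose realised rate is well below nominal. D is a no-influence hypothesis, so a significant D contradicts it and is not a success. B asks about testing intervals and could not be presented as the regimen or exposure result. In the real dispute, A against C, the inflation is negligible.

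Finally, A cannot by itself separate a gel effect from a plain regimen difference. This also stands: naming A without touching 2.1 would leave the stated primary objective with no primary test.

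**Conclusion.** The point holds as an ambiguity in the primary comparison. The protocol refers to one, does not name it, and points to A in some places and C in another; if they disagree, the trial's verdict is undefined. This needs no arithmetic.

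Error inflation is a secondary matter. Across the four tests it is about 6-11% at common failure rates of 20-50%. At 5-10% it is 0.5-2.1% under the rule that matches the stated powers, or 2.6-6.1% under the usual Fisher p-value. For A or C alone it is at most about 5-6%.

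These figures assume the planned group sizes, one failure rate in all groups, and no count for the Mantel-Haenszel test. The SAP may name a primary comparison; the protocol would still need to agree with it.

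**What to change.** In 9.1 and 9.3, label one comparison as the single primary test at two-sided 0.05. A is the one that the overview, Table 1 and the randomisation support.

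Align objective 2.1 with that choice: word it as the randomised comparison of regimens in gel-exposed women, and state that C addresses the exposure effect as non-randomised supportive evidence.

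Report B, C and D as risk differences with 95% confidence intervals and no confirmatory claim.

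**Cost:** wording in 2.1, 9.1, 9.3 and the SAP. A keeps its 70% power, against 49% under Bonferroni. B, C and D lose confirmatory status, which 25-43% power could hardly carry. If the sponsor regards the exposure question as the main one, it can label C instead and leave 2.1 as it is, but must then accept a non-randomised primary comparison with 43% power.
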